7.4.1. Human Chorionic Gonadotropin Tests

Human chorionic gonadotropin tests in urine will be performed for all female patients who have reached puberty and achieved menarche at the SV and, if clinically indicated, thereafter. Any female patient who becomes pregnant during the study will be withdrawn. Procedures for reporting the pregnancy are provided in Section 7.2.

7.5. Physical Examinations

Physical examinations, including weight and height, will be performed at the time points detailed in Table 3. Any physical examination finding that is judged by the investigator as clinically significant will be considered an adverse event, recorded on the CRF, and monitored as described in Section 7.1.2.

7.6. Vital Signs

Vital signs (blood pressure [BP] and pulse) will be measured at the time points detailed in Table 3. All vital signs results outside of the reference ranges will be judged by the investigator as belonging to 1 of the following categories:

- abnormal but not a clinically significant worsening from baseline

- abnormal and a clinically significant worsening from baseline

Before BP and pulse are measured, the patient must be in a supine or semi-erect/seated position and resting for at least 5 minutes (the same position and arm should be used each time vital signs are measured for a given patient). For any abnormal vital sign finding, the measurement should be repeated as soon as possible. Any vital sign value that is judged by the investigator as clinically significant will be recorded on the source documentation, transcribed to the CRF as an adverse event, and monitored as described in Section 7.1.2.

In addition, potentially clinically significant values may be predefined by the sponsor for selected vital signs (see Section 9.7) and, if so, will be documented in the statistical analysis plan or other relevant documents (eg, medical monitoring plan).

7.7. Oropharyngeal Examinations

Oropharyngeal examinations will be performed at every visit (SV through TV6). The examination must be performed by a qualified healthcare professional. Whenever possible, the same qualified healthcare professional should complete the assessment for the same patient throughout that patient's participation in the study.

Patients with clinical visual evidence of oral candidiasis at SV who agree to receive treatment and comply with appropriate medical monitoring may participate in the run-in period and may return for randomization. However, if the oral candidiasis is not controlled at that time, the patient will not be allowed to enter the study treatment period.

Any visual evidence of oral candidiasis during the treatment period of the study (after RV through TV6, inclusive) will be evaluated by obtaining and analyzing a swab of the suspect area. Appropriate therapy should be initiated immediately at the discretion of the investigator and should not be delayed for culture confirmation.

Patients with a culture-positive infection may continue participation in the study on appropriate anti-infective therapy, provided this therapy is not prohibited by the protocol. If a patient requires a protocol-prohibited medication for therapy, the patient will be discontinued from the study and provided appropriate therapy.

**8. ASSESSMENT OF PHARMACOKINETICS /
PHARMACODYNAMICS / BIOMARKERS /
PHARMACOGENOMICS / IMMUNOGENICITY / ANCILLARY
STUDIES**

8.1. Pharmacokinetic Assessment

Pharmacokinetic parameters are not evaluated in this study.

8.2. Pharmacodynamics Assessment

Pharmacodynamic parameters are not evaluated in this study.

8.3. Assessment of Exploratory Biomarkers

Biomarkers are not evaluated in this study.

9. STATISTICS

This section describes the statistical analysis planned for this study. Changes, additions, and further details about the analyses will be described in the statistical analysis plan (SAP). After finalization of the statistical analysis plan, any additional analyses or changes to analyses that may be required will be fully disclosed in the CSR.

9.1. Sample Size and Power Considerations

Sample size and power calculations are driven by demonstrating superiority of FS MDPI 50/12.5 mcg twice daily over Fp MDPI 50 mcg twice daily in change from baseline in 1-hour postdose percent predicted morning FEV₁ at week 12 and the superiority of Fp MDPI 50 mcg twice daily over placebo in change from baseline in percent predicted trough morning FEV₁ at week 12.

For the superiority comparison of FS MDPI 50/12.5 mcg twice daily versus Fp MDPI 50 mcg twice daily, assuming that the change from baseline in 1-hour postdose percent predicted morning FEV₁ at week 12 is analyzed using an ANOVA model with only a single factor of treatment group, the following assumptions were made:

- The initial assumed common standard deviation (SD) was 9.3% and the true treatment difference was 4.5% between FS MDPI 50/12.5 mcg twice daily and Fp MDPI 50 mcg twice daily. This assumption was based on data collected in previous Teva studies with the same Fp MDPI and FS MDPI products in adult asthma patients who completed the 12-week treatment period and based on office-based spirometry.
- The initial power was 97% at a 2-sided significance level of 5%.

For the superiority comparison of Fp MDPI 50 mcg twice daily versus placebo, assuming that the change from baseline in percent predicted trough morning FEV₁ at week 12 is analyzed using an analysis of variance (ANOVA) model with only a single factor of treatment group, the following assumptions were made:

- The initial assumed common standard deviation (SD) was 13.25% and the true treatment difference was 5% between Fp MDPI 50 mcg twice daily and placebo. This assumption was based on data collected in previous Teva studies with the same Fp MDPI product in adult asthma patients and based on office-based spirometry
- The initial power was 85% at a 2-sided significance level of 5%.

This study FSS-AS-30003 is the first Teva's study in which the handheld spirometry is utilized as an endpoint and this handheld device is being used in a pediatric asthma patient population, the target population of this study. A blinded sample size reassessment was not planned for this study. However, routine blinded data monitoring of this study FSS-AS-30003 revealed that a few patients showed nonphysiologic (~200% of percent predicted FEV₁) changes from baseline. This triggered a blinded sample size reassessment that showed that the overall mean change from baseline and SD for the overall study population is higher than the initial assumptions based on the office spirometry in adult asthma patients. In addition, monitoring of FEV₁ stability throughout the study revealed challenges in obtaining consistent morning trough FEV₁ values with best efforts in this young patient population, despite the rigorous training and coaching

provided by the investigators. Therefore, some of the initial assumptions and the sample size described above were revised to the following:

- For the superiority comparison of FS MDPI 50/12.5 mcg twice daily versus Fp MDPI 50 mcg twice daily, the SD was revised to 22% and the overall mean change from baseline was revised to 6.5% (blinded SD observed after 427 patients completed week 12 of this study (excluding IMPD)) and the power down to 80%.
- With these assumptions, 181 patients per treatment group are required for the 2-sided test of FS MDPI 50/12.5 mcg twice daily and Fp MDPI 50 mcg twice daily.
- For the superiority comparison of Fp MDPI 50 mcg twice daily versus placebo, the SD was revised to 17% and overall mean change from baseline was 5% (blinded SD observed after 434 patients completed week 12 of this study (excluding IMPD)) and the power was revised to 80%.
- With these assumptions, 181 patients per treatment group are required for the 2-sided test of Fp MDPI 50 mcg twice daily versus placebo.

Assuming a dropout rate of 12%, then 206 patients per treatment group in the 4 treatment groups, for a total of 824 patients, will be randomized (initial assumption for dropout rate was 15%).

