9.6. Multiple Comparisons and Multiplicity

A fixed-sequence testing procedure will be employed to control the overall Type I error rate at the 2-sided 0.05 level for the co-primary endpoints. The sequential order of comparisons will be as follows:

1. 1-hour postdose percent predicted FEV₁ comparing FS MDPI 50/12.5 mcg versus Fp MDPI 50 mcg
9. Trough percent predicted FEV₁ comparing Fp MDPI 50 mcg versus placebo
10. Trough percent predicted FEV₁ comparing Fp MDPI 25 mcg versus placebo

Each test will be 2-sided and performed at the 0.05 level of significance. However, if a test is not significant at the 2-sided 0.05 level, no further tests will be performed.

Taking into consideration that this is the very first study that utilizes the handheld device in a large Phase 3 study in a pediatric asthma patient population (4 to 11 years of age), an unplanned blinded sample size reassessment was conducted. Since the adjustment to sample size was based on blinded standard deviation, no adjustment to the multiplicity control is warranted.

Multiplicity control for the secondary endpoints and the sequential order of the secondary endpoints will be described in the statistical analysis plan.

No multiplicity adjustments will be made for other efficacy analyses.

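### The revised sample size treats the blinded pooled mean change (6.5%) as the FS-versus-Fp difference; at the only sourced difference, 4.5 points, the gatekeeping test has about 49% power, not 80%

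*Protocol*

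**What the plan says.** Protocol section 9.1 starts from an assumed SD of 9.3% and states that "the true treatment difference was 4.5% between FS MDPI 50/12.5 mcg twice daily and Fp MDPI 50 mcg twice daily", with 97% power. The source given is earlier adult studies with office spirometry. This is the only FS-minus-Fp difference in either document.

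After an unplanned blinded reassessment, the same section reports that "the SD was revised to 22% and the overall mean change from baseline was revised to 6.5" percent, from 427 patients who had completed week 12, "and the power down to 80" percent. For the comparison with the Fp 50 arm it then states: "With these assumptions, 181 patients per treatment group are required for the 2-sided test of FS MDPI 50/12.5 mcg". Allowing 12% dropout gives 206 randomized per arm, 824 in total. The section says that the mean and SD from the reassessment are those of the overall study population. The synopsis and SAP section 2.4 repeat the figures.

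Protocol section 9.6 and SAP section 7.1 put FS 50/12.5 versus Fp 50 first in the fixed sequence. Both also say of the resizing: "Since the adjustment to sample size was based on blinded standard deviation, no adjustment to the multiplicity control is warranted".

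**The concern.** A power calculation for comparing two arms needs a difference between those arms. The revised text gives an SD and a pooled within-patient change, but no difference. A blinded mean over four arms cannot supply one: it would be 6.5 if every arm were identical, and also if the arms differed widely. If 6.5 took the place of 4.5 in the calculation, the SD was raised from 9.3 to 22 while the effect was also raised by 2 points, with no source for the second change.

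The stakes go beyond one comparison. If the FS test misses 0.05, protocol section 9.6 stops all further testing, and SAP section 7.1 allows no inferential reading of later comparisons. The power of this test is therefore an upper limit on the probability of a confirmatory claim for either Fp dose. Readers of the plan are told that this limit is 80%.

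**Working it through.** **Inputs.** Two-sided 5% (protocol 9.6: "Each test will be 2-sided and performed at the 0.05 level of significance"); equal allocation; unadjusted comparison of means (protocol 9.1 assumes a one-factor ANOVA). Initial values: 4.5/9.3 for FS versus Fp and 5/13.25 for Fp versus placebo, with 127 evaluable per arm (the 127 is from the amendment summary and serves only to check the formula). Revised values: 6.5/22 and 5/17, with 181 evaluable per arm.

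**Formula.** SE = SD × √(2/n). The ratio of the difference to the SE is the noncentrality of a two-sample t test on 2n − 2 degrees of freedom, and power comes from the noncentral t.

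**Step 1: check the formula on the initial figures.**
- 4.5/9.3, n = 127: SE = 1.167, ratio 3.86, power 97.0%. The plan says 97%.
- 5/13.25, n = 127: SE = 1.663, ratio 3.01, power 85.0%. The plan says 85%.

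**Step 2: find what produces 181.**
- 6.5/22, n = 181: SE = 22 × √(2/181) = 2.313, ratio 2.81, power 80.05%. At n = 180 it is 79.8%, so 181 is the smallest n that reaches 80%.
- 181/0.88 = 205.7, rounded up to 206. The plan says 206.
- Working backwards (normal approximation), the difference detectable with 80% power is (1.960 + 0.842) × 2.313 = 6.48.
- 5/17 for Fp versus placebo, n = 181: power 79.7% (183 needed for 80%). Here the reported overall mean change equals the original 5-point difference, so the assumed effect does not change.

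The documents do not say outright that 6.5 was entered as the difference. But it is the only revised quantity apart from the SD and the power, and it returns 181 exactly.

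**Step 3: put in the stated difference.**

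| Difference | SD | n per arm | Power |
|---|---|---|---|
| 4.5 | 22 | 181 | 49.2% |
| 4.5 | 22 | 206 | 54.4% |
| 4.5 | 22 | 377 | 80.1% |

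A one-sided 5% test does not explain the figure either: 4.5/22 would give 61.8% at 181 and need 296 per arm (normal approximation).

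**Step 4: sensitivity to the SD.** At 4.5 points and n = 181, assumed SDs of 20, 18, 17 and 15 give 57%, 66%, 71% and 81%.

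**Step 5: effect on the sequence.** The FS and Fp 50 tests share the Fp 50 arm, so their statistics have correlation −0.5ρ, where ρ is the within-patient correlation of the two endpoints. The documents do not give ρ; I assume 0 to 0.7. Probability of winning both tests, from a bivariate normal:
- differences 6.5 and 5: 61.7% to 64.1%;
- differences 4.5 and 5: 35.5% to 39.5%.

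The plan reports neither range.

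**The case against.** The strongest reply has four parts.

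**The 4.5 is an initial adult value, and the amendment says some initial assumptions were revised.** Pairing it with a paediatric SD mixes two sources, and the pooled-mean label may simply be a misnomer for a new assumed difference. This cannot be excluded, but the text describes the mean as that of the overall study population, and no paediatric FS-minus-Fp difference or source appears anywhere. The defect would then be an unsourced effect of 6.5 points, and the remedy is the same. It is fair to call 4.5 the only sourced difference rather than the current one.

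**SD 22 may be too large for the planned analysis.** A few nonphysiologic values triggered the reassessment. SAP section 4.1 sets percent predicted values of 200% or more to missing, and the primary model is an ANCOVA with baseline. The documents do not say whether SD 22 includes those values. If it does, and one, two or three of the 427 patients had changes near 200 points, removing them gives SDs of 19.9, 17.6 and 14.8 and power of 57%, 68% and 82%. If the changes were nearer 115 to 130 points (a 200% value against a baseline of 70% to 85%), power is 51% to 59%. This caveat stands: 49% is the power at the plan's own SD, and 80% is recovered only near an SD of 15. The plan makes no such argument.

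**The resizing sentence does not say that only the SD was used.** True. It names only the SD, and a blinded pooled mean reveals no treatment assignment, so its conclusion on multiplicity is not disturbed. The sentence is incomplete; I do not suggest that Type I error is inflated.

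**Fp results would still be available if the FS test failed.** Yes, as estimates under SAP section 7.1, but not as confirmatory claims.

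**Conclusion.** The concern holds and should be corrected before the plan is relied on. The 80% is correct arithmetic for a true difference of 6.5 points, but nothing in the documents supports 6.5 as a difference between FS and Fp. At the only sourced difference, with the plan's own SD of 22, two-sided 5% and unadjusted comparison, power for the first test is about 49% with 181 per arm and 54% with 206. The number needed for 80% is 377 evaluable per arm, about twice the plan's figure. Under those same inputs, the probability of also securing the Fp 50 claim is roughly 36% to 40%, against 62% to 64% on the plan's own figures.

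That 6.5 was entered as the difference is inferred from an exact numerical match, not from an explicit statement. A smaller SD in the final analysis, or a larger true effect in children, would raise these figures; neither is documented as a planning assumption.

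**What to change.** 1. In protocol section 9.1, the synopsis and SAP section 2.4, state the assumed FS-minus-Fp difference separately from the blinded pooled mean change. Either give a source for 6.5 points as a between-arm difference, or report about 49% power at 4.5 points and SD 22, with 80% reached only if the true difference is about 6.5.
2. State whether SD 22 includes values that SAP section 4.1 will set to missing. If a smaller SD is thought to apply, give it with the resulting power.
3. State the probability of reaching and winning the Fp 50 versus placebo test under the fixed sequence, with the assumed endpoint correlation.
4. In protocol section 9.6 and SAP section 7.1, say that the resizing used the blinded SD and also replaced the effect input, if that is what was done. The conclusion that no multiplicity adjustment is needed can rest on the blinding.

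The cost is wording only. No patients are added and no analysis or test order changes; the stated power becomes less favourable.

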9.2. Analysis Sets

9.2.1. Intent-to-Treat Analysis Set

The intent-to-treat (ITT) analysis set will include all randomized patients.

In the ITT analysis set, treatment will be assigned based on the treatment to which patients were randomized, regardless of which treatment they actually received.

The ITT analysis set will serve as the primary analysis set for efficacy analyses.

9.2.2. Safety Analysis Set

The safety analysis set will include all randomized patients who receive at least 1 dose of IMP.

In the safety analysis set, treatment will be assigned based on the treatment patients actually received, regardless of the treatment to which they were randomized, unless otherwise specified.

The safety analysis set will be used for all analyses of safety data.

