3. STUDY DESIGN

3.1. General Design and Study Schematic Diagram

This is a Phase 3, 12-week, multicenter, randomized, double-blind, parallel-group, placebo-controlled study to evaluate the safety and efficacy of Fp MDPI and FS MDPI administered twice daily at doses of Fp MDPI 25 mcg, Fp MDPI 50 mcg, and FS MDPI 50/12.5 mcg in pediatric patients with asthma. The total duration of patient participation in this study is approximately 15 to 17 weeks depending on the duration of the placebo run-in period.

Patients meeting all of the inclusion criteria and none of the exclusion criteria at the screening visit (SV) will begin a 14- to 30-day run-in period. An albuterol/salbutamol hydrofluoroalkane (HFA) metered-dose inhaler (MDI) (a SABA inhaler) will be provided to replace the patient's current rescue medication and is to be used as needed for relief of asthma symptoms during the run-in and treatment periods, with a maximum of 12 inhalations permitted per day. Starting day 1 of the run-in period, patients must discontinue all nonstudy asthma-related drugs and instead take a patient-blinded MDPI placebo device (1 inhalation twice daily).

The study consists of 3 periods as follows:

- Patient-blinded run-in period: SV to RV, up to 30 days
- Double-blind, randomized treatment period: RV through the TV6, approximately 12 weeks
- Follow-up period: TV6 through the follow-up visit (FV), approximately 7 days after TV6

A prescreening visit may be conducted, if needed, before the SV to discuss study procedures and/or provide patient instructions about any required washout periods for prohibited medications. SV may take place during several investigational center visits.

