Patients who qualify for entry into the placebo run-in period must discontinue all currently administered asthma medications (including leukotriene modifiers prescribed for other conditions) until completion of the TV6 (week 12) visit or IMPDV if, in the investigator's judgment, there would be no inherent harm in changing the patient's treatment and the patient or parent/legal guardian provides consent/assent (as applicable). Patients will be provided with albuterol/salbutamol HFA MDI (90 mcg ex-actuator) or equivalent as rescue medication. During the run-in period (SV to RV), in addition to the above rescue medication, patients will be provided with a patient-blinded placebo MDPI device for twice-daily use after appropriate training and demonstration of proper technique.

All patients who enter the placebo run-in period will perform daily morning and evening lung function assessments (FEV₁ and PEF) by handheld device at home and assess and record daytime and nighttime asthma symptom scores, rescue albuterol/salbutamol HFA MDI use, and morning and evening IMP dosing in the patient diary built into the handheld device.

Patients who experience an URI or lower respiratory infection (LRI) during the run-in period should be classified as randomization failures and be discontinued from the study but may be rescreened 2 weeks after resolution of the infection. Patients who are rescreened will need to repeat all screening procedures and evaluations. Only 1 rescreening for each patient will be permitted.

Patients who entered the run-in period with response to a bronchodilator $\geq 10\%$ and $< 14.50\%$ must present for repeat lung function assessments and another bronchodilator test within 14 ± 2 days, during which they must demonstrate at least a 15% response to a bronchodilator. If

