- q. The patient has had no significant changes in asthma medications during run-in, excluding the albuterol/salbutamol HFA MDI (90 mcg ex-actuator) or equivalent used as rescue medication or run-in placebo MDPI as supplied per protocol.
- r. The patient has not had a URI or LRI during the run-in period. Patients who develop a URI or LRI during the run-in period may be discontinued from the study and allowed to rescreen 2 weeks after resolution of symptoms.
- s. The patient has had no asthma exacerbation during the run-in period, defined as any worsening of asthma requiring any significant treatment other than rescue albuterol/salbutamol HFA MDI (90 mcg ex-actuator) or equivalent or the patient's

- run-in MDPI. This includes requiring the use of systemic corticosteroids, inhaled corticosteroids or other medications used to control asthma or are prohibited medications ([Appendix H](#)), and/or ER/urgent care clinic visit or hospitalization. Note: A single dose of nebulized albuterol/salbutamol will not meet the criteria for an asthma exacerbation. Emergency room/urgent care clinic visits where the treatment is limited to a single dose of nebulized albuterol/salbutamol will not meet the criteria of an asthma exacerbation.
- t. The patient has no clinical visual evidence (on oropharyngeal examination) of oropharyngeal candidiasis.
 - u. The patient has not experienced an adverse event that would result in failure to continue to meet selection criteria.
 - v. The patient has not used any of the prohibited concomitant medications during the run-in period (see Section [5.7](#) and [Appendix H](#)).
 - w. The patient has complied with home lung function assessments and patient diary (built into the handheld device) entry on at least 5 of the last 7 days prior to RV, including the following:
 - completion of daytime and nighttime asthma symptom scores
 - completion of daytime and nighttime rescue medication (albuterol/salbutamol HFA MDI) use (whether used or not)
 - completion of the morning and evening lung function assessments (FEV₁ and PEF) by handheld device on 5 or more of the 7 days immediately preceding the RV
 - recording of morning and evening IMP use on 5 or more of the 7 days immediately preceding RV

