If data are processed from other sources (eg, central laboratory, bioanalytical laboratory, central image center, data from the patient diary built into the handheld device, electronic patient-reported outcome [ePRO] tablet), these data will be sent to the investigational center, where they will be retained but not transcribed to the CRF, unless otherwise noted in the protocol. These data may also be sent electronically to the sponsor (or organization performing data management). All patient data must have supportive original source documentation in the medical records, or equivalent, before they are transcribed to the CRF. Data may not be recorded directly on the CRF and considered as source data unless the sponsor provides written instructions specifying which data are permitted to be recorded directly to the CRF.

For patients who enter a study but do not meet entry criteria, at a minimum, data for screening failure reason, demography, and adverse events from the time of informed consent will be entered in the CRF.

Data Quality Control

Data Management is responsible for the accuracy, quality, completeness, and internal consistency of the data from this study. Oversight will be carried out as described in the sponsor's SOPs for clinical studies. Day to day data management tasks for this study are delegated to a contract organization, and these functions may be carried out as described in the SOPs for clinical studies at that organization. These SOPs will be reviewed by the sponsor before the start of data management activities.

Data will be verified by the study monitor using the data source, and reviewed by Data Management using both automated logical checks and manual review. Data identified as erroneous, or data that are missing, will be referred to the investigational center for resolution through data queries. Any necessary changes will be made in the clinical database, and data review and validation procedures will be repeated as needed. Data from external sources will be compared with the information available in the CDMS and any discrepancies will be queried.

Applicable terms will be coded according to the coding conventions for this study.

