8. SAFETY ANALYSIS

8.1. General

The safety analysis set will be used for all safety analyses. Summaries will be presented by treatment group and will represent what treatment was actually received, unless specified otherwise. Summaries of clinically significant abnormal values will include all postbaseline values (including scheduled, unscheduled, and IMPDV).

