8.4. Adverse Events

All adverse events will be coded using the MedDRA version 19.0. The incidence of adverse events will be summarized using descriptive statistics (counts and percentages) by SOC and preferred term (PT). Patients are counted only once in each SOC category, and only once in each PT category. Treatment-related adverse event summaries will include adverse events with missing relationship to study drug. For the summaries by severity, patients are counted at the greatest severity. Summaries will be presented for all treatment-emergent adverse events (overall and by severity), treatment-emergent adverse events determined by the investigator to be related to IMP (see FSS-AS-30003 protocol Section 7.1.4) (defined as related or with missing relationship, overall and by severity), serious treatment-emergent adverse events, treatment-emergent adverse events causing withdrawal from the study, and nonserious adverse events. Summaries will be presented by treatment group and for all patients.

Any event occurring after the patient has signed the study informed consent/assent form should be recorded and reported as adverse event. Those events occurring prior to the first dose of IMP will be considered as non-treatment-emergent adverse events, and those occurring on or after the first dose of IMP drug through 7 days after the last dose of IMP will be considered as treatment-emergent adverse events. Any events that occurred beyond the 7 days after the last dose of IMP will be considered as non-treatment-emergent adverse events.

For all non-treatment-emergent adverse events that occurred during the run-in period, a summary and a patient listing will be presented separately. All non-treatment-emergent adverse events that occurred 7 days after the last dose of IMP, prior to week 12 (mainly for patients who discontinued IMP but continued in the study) will be presented similarly. In addition, serious adverse events that were reported during the follow up period will be presented.

For all treatment-emergent adverse events that lead to discontinuation from IMP treatment through 7 days after the last dose of IMP will be summarized.

Patient listings of deaths, serious adverse events, adverse events leading to discontinuation, MedDRA dictionary terms for adverse event descriptions, and adverse event PT by patient number will be presented.

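### Taken literally, the planned run-in adverse event summary covers randomized children only, so it omits those kept out of randomization by a run-in exacerbation, respiratory infection or disqualifying adverse event

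*Protocol*

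**What the plan says.** - **Safety population.** Protocol 9.2.2: "The safety analysis set will include all randomized patients who receive at least 1 dose of IMP". It goes on: "The safety analysis set will be used for all analyses of safety data". SAP 3.2 repeats both statements, and SAP 8.1 opens the safety section with "The safety analysis set will be used for all safety analyses".
- **Run-in output.** SAP 8.4: "For all non-treatment-emergent adverse events that occurred during the run-in period, a summary and a patient listing will be presented separately". It names no population.
- **What happens in the run-in.** Protocol 3.1: from day 1, "patients must discontinue all nonstudy asthma-related drugs and instead take a patient-blinded MDPI placebo device". The run-in lasts 14 to 30 days.
- **Who may be randomized.** Protocol 5.9, criterion s: "The patient has had no asthma exacerbation during the run-in period". That criterion counts an ER or urgent care visit or a hospitalization as an exacerbation, except a visit limited to a single nebulized dose. Criterion r bars a URI or LRI, and criterion u bars an adverse event that breaks eligibility. Protocol 3.1 says children with a run-in URI or LRI "should be classified as randomization failures and be discontinued from the study".
- **What is collected.** For patients who fail entry criteria, Protocol Appendix K says "adverse events from the time of informed consent will be entered in the CRF".

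**The concern.** Adverse event incidence throughout the study is a safety endpoint (Protocol 2.1). Events count from consent, and the adverse event definition in Protocol 7.1.1 includes those arising in a washout phase. The run-in is such a phase: children aged 4 to 11 give up their controllers because the protocol requires it.

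The plan recognises this by promising a run-in summary. Its general rule then confines that summary to children who passed the randomization criteria, several of which are themselves safety events. The result is a survivor-only summary. At stake is whether the study report gives the incidence of adverse events and SAEs among all children exposed to the run-in, or only among those who came through it without a disqualifying event.

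**Working it through.** The plan states no run-in event figure, so there is none to reproduce. The check sets the passages side by side.

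**Step 1: which population governs SAP 8.4?** Protocol 9.2.2 and SAP 3.2 and 8.1 each say the safety set is used for every safety analysis. The exception clauses in Protocol 9.2.2 and SAP 8.1 attach to how treatment is assigned or presented, not to who is included. By contrast, SAP 5.2 says outright that the disposition summary extends to all screened patients. SAP 8.4 makes no such extension, so SAP 8.1 applies.

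**Step 2: can a child with the event be in that population?**

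| Run-in event | Rule | In the safety set? |
|---|---|---|
| Exacerbation, including a serious one | Criterion s | No |
| URI or LRI | Criterion r; Protocol 3.1 | No, except a rescreened child's earlier attempt |
| Adverse event that breaks eligibility | Criterion u | No |
| Milder, non-disqualifying adverse event | None | Yes, if the child is later randomized |

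The safety set lies within the randomized set. The first three rows are excluded from the randomized set, apart from protocol deviations. Their expected count in the run-in summary is therefore close to zero at any true event rate.

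**Step 3: does another output fill the gap?**

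- Disposition (Protocol 9.4.1, SAP 5.2) counts children who entered the run-in and were not randomized, with the reason, and adds a by-patient listing. It plans no severity, seriousness, timing or outcome. Its percentages use randomized patients as the denominator, so it gives no rate among entrants.
- The exacerbation tables (SAP 8.6) are by treatment group, which a non-randomized child does not have.
- Deaths get a listing and narrative (Protocol 9.7, SAP 8.5), and SAEs reach the sponsor within 24 hours (Protocol 7.1.5.3.1). Neither yields run-in incidence.

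**Step 4: scale, as illustration only.** The planned randomized total reproduces: 181 / (1 − 0.12) = 205.7, rounded up to 206 per arm, and 4 × 206 = 824. Suppose a share p of run-in entrants fails for exacerbation or respiratory infection and all others are randomized. Entrants are then 824 / (1 − p), and the number omitted is that minus 824. The values of p are assumptions.

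| p | Entrants | Omitted |
|---|---|---|
| 1% | 832.3 | about 8 |
| 2% | 840.8 | about 17 |
| 5% | 867.4 | about 43 |
| 10% | 915.6 | about 92 |
| 15% | 969.4 | about 145 |

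**The case against.** The best counter-argument is that SAP 8.4 speaks of *all* run-in events and presents them separately. A specific sentence can override a general one, and the authors may have meant everyone who entered the run-in. That reading is possible, and it is why the point concerns the literal text. But three passages say the opposite, so the population should be named rather than inferred.

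It is also fair that the safety objective concerns the test products, that no test drug is given in the run-in, and that a randomized-and-dosed set is right for comparing arms. This stands, and the fix leaves that set alone. It does not answer the promise of a run-in summary.

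Three further points limit the finding:

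- **Non-serious exacerbations** are not adverse events in this study (Protocol 7.1.1). They would be missing from an adverse event summary on any population, so changing the population alone does not recover them.
- **Candidiasis** does not belong with the excluded events. Criterion t applies at the randomization visit, and Protocol 7.7 lets a child treated after screening return for randomization if it is controlled by then.
- **Oversight is not missing.** SAEs are collected from consent and reviewed as they are reported. The gap is in tabulation.

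**Conclusion.** The point holds as a reporting gap. Under the plan's stated rule, the run-in summary omits the children whose run-in respiratory infection, exacerbation or other disqualifying event kept them from randomization. The conclusion assumes that SAP 8.1 governs 8.4 and that the criteria are applied as written. The efficacy analyses and the comparisons between arms are unaffected.

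The size cannot be stated, because the documents give neither a run-in failure rate nor a run-in event rate.

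A reader might infer more, and the documents do not support it:

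- *That the report would make the run-in look event-free.* Disposition reasons, the disposition listing, death reporting and individual SAE reports would show otherwise, and milder events in randomized children would still appear.
- *That a complete table would show the harm of stopping controllers.* The run-in has no concurrent control, so even full counts are descriptive.
- *That the omission can be sized from the earlier placebo arm in SAP 6.2, where 9.3% withdrew for worsening asthma.* That figure comes from randomized patients aged 12 and older over 6 weeks. It counts treatment withdrawals, not exacerbations or SAEs as defined here. Carrying it to this run-in needs a constant rate and a failure fraction that the documents do not provide.

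**What to change.** - In Protocol 9.2 and SAP 3, define a run-in safety set: all children dispensed the run-in placebo MDPI, randomized or not.
- In SAP 8.1 and 8.4, name it as the population for the run-in summary and listing of adverse events, SAEs and deaths, split by whether the child was randomized.
- Tabulate run-in exacerbations separately on the same set, because the non-serious ones are not adverse events.
- Label the output descriptive, and keep the present safety set for treatment-emergent tables by arm.

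The cost is one more table and listing. Adverse events are already entered in the CRF from consent. For non-serious run-in exacerbations, check what the CRF holds: the exacerbation entry in Protocol 3.1 is not limited to the treatment period, but part of the detail it asks for is tied to the IMP discontinuation visit. The other cost is that the reported run-in event rate will look less favourable. Conduct, power and the primary analysis do not change.
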